7.2. Patient assessment

Patient reported assessments will be performed using commonly used, validated questionnaires:

- 1. EQ-5D questionnaire completed at: baseline (at recruitment); after surgery; and 3 , 6, and 12 months after randomisation.
- 2. Cost collection form for health resource usage, completed at baseline, 3, 6, and 12 months after first FNAC
- 3. Visual analogue pain score after every FNAC.
- 4. Hospital depression and anxiety score (HADS) questionnaire completed at: baseline; , 3, 6, and 12 months after randomisation.

Where possible, patient questionnaires should be completed when patients are attending hospital appointments. If this is not feasible, the questionnaires should be posted by a member of the research team at site, to the patient for completion at home.

7.3. Complication rates

Complication rates following thyroid operations will be recorded at 30 days and 6 months postsurgery.

Data will be collected on haematoma rate and temporary hypocalcaemia rate at 30 days and vocal cord palsy and permanent hypocalcaemia at 6 months post-surgery only.

7.4. Timing of assessments

Assessment Schedule	Prior to trial entry	Baseline prior to first FNAC	Immediately after any FNAC	After FNAC result	After surgery	30 days post-op	3 months post- randomisation	3 months post-op	6 months post-op	6 months post- randomisation	12 months post-op	12 months post- randomisation
Written Informed consent	Х											
Review inclusion / exclusion criteria	Х											
EQ-5D		Х			Х		Х			Х		X
Hospital Anxiety and Depression Scale (HADS)		Х					Х			Х		х
Cost collection CRF					Х		Х			Х		Х
Blood sample collection		Х						Х			Х	
Tissue sample collection*			Х		Х							
Histology Assessment CRF **					X							
Visual Analogue Pain Score			Х									
FNAC Assessment CRF			X									
FNAC Result CRF***				Χ								
Surgical Decision Form				Х								
Surgery and surgical complications CRF****						х			х			

- * Cytology and Histology. Please refer to tissue collection guidelines on page 17.
- **The accompanying histopathology report should also be sent with the completed histology assessment CRF.
- ***The accompanying radiology report should also be sent with the completed FNAC result form.
- **** Completed using the 30-day Post-Operative Assessment CRF and 6-month Post-Operative Assessment CRF.

7.5. QUALITY ASSURANCE

Radiology

The first 5 US elastography scans of each radiologist will be reviewed by one of the Trial Radiology Panel ([name] and [name]). Thereafter, a random sample of 10% of all scans will be reviewed by the Trial Radiology Panel. Discordances will be fed back to the relevant radiologists.

Cytology and histology

All Thy 3a, 3f, 4 & 5 FNACs and a random sample of 5% of all Thy 1 & Thy 2 FNACs and all thyroidectomy histological samples will be reviewed by one of the experienced thyroid cyto/histopathologists of the Trial's Reference Pathology laboratory.

7.6. Data handling and record keeping

7.6.1 Source data

Data should be collated directly from the patient (for Quality of Life and cost collection questionnaires) or from the patient hospital notes using the ELaTION case report forms. Within the ElaTION trial, source data is the participant's medical notes generated and maintained at site.

7.6.2 CRF completion

In all cases it remains the responsibility of the Investigator to ensure that the CRF has been completed correctly and that the data are accurate.

Data reported on each CRF should be consistent with the source data or the discrepancies should be explained. If information is not known, this must be clearly indicated on the CRF. All missing and ambiguous data will be queried. All sections are to be completed.

7.6.3 Data management and validation

Data will be collected via paper CRFs: paper forms should be sent to the ELaTION Trial Office for central input. Data validation is built into the database, so that range, date and logic checks are performed at the point of data entry.

CRFs these must be completed, signed/dated and returned to the ELaTION Trial Office by the Investigator or an authorised member of the site research team (as delegated on the ELaTION Trial Signature & Delegation Log) as soon as possible. Entries on paper CRFs should be made in ballpoint pen, in black ink, and must be legible. Any errors should be crossed out with a single stroke, the correction inserted and the change initialled and dated. If it is not obvious why a change has been made, an explanation should be written next to the change.

Email and letter reminders will be sent to the investigator and research coordinator for missing CRFs; Data Clarification Forms (DCFs) will be sent to request missing data or to resolve data inconsistencies.

7.7. Definition of the End of Trial

The end of the trial will be 6 months after the last data capture, i.e. 6 months after the date of the last visit of the last patient undergoing protocol based treatment. Within ElaTION, the last visit is once the last participant has reached 1 year follow-up.

However, patients will be asked for permission to monitor long-term survival and recurrence rates through medical interventions, HES, ONS, cancer and other registry data and GP information.

The Trials Office will notify the REC the trial has ended and a summary of the clinical trial report will be provided within 12 months of the end of trial.

A copy of the end of trial notification as well as the summary report is also sent to the University of Birmingham Research Governance Team at the time these are sent to the REC.

8. STATISTICAL CONSIDERATIONS

8.1. Outcome Measures

The reference standard for all FNAC assessments and results is the final definitive diagnosis.

Final definitive diagnosis is defined as:

- obtaining two benign (Thy 2) FNAC results;
- or obtaining one Thy2 FNAC with a U2 scan;
- or obtaining histopathological diagnosis following a Thy 3, Thy 3f, Thy 4, or Thy5 result;
- or obtaining histopathological diagnosis following persistently non-diagnostic (Thy 1) FNAC results.

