11.6. Confidentiality of Personal Data	
11.7. Publication	
REFERENCE LIST	27

ELATION TRIAL SUMMARY

Trial design: Pragmatic randomised controlled trial with 1:1 randomisation.

Objectives: The primary objective is to determine if real time elastography (RTE) in conjunction with fine needle aspiration cytology (FNAC) will reduce the number of patients who have a non-diagnostic **first** FNAC result as compared to conventional ultrasound (US) only guided FNAC.

Outcome measures

Primary outcome measure

The proportion of patients who have a non-diagnostic (Thy1) cytology result following the first FNAC.

Secondary Outcome measures

- 1. Number of FNACs required to obtain a definitive diagnosis¹;
- 2. Time from first FNAC to obtaining a definitive diagnosis;
- 3. The proportion of patients with benign histology results following thyroidectomy;
- 4. Proportion of patients who have thyroidectomy;
- 5. Accuracy of a cytology result for first FNAC and repeated FNAC in relation to overall definitive diagnosis;
- 6. Accuracy of an imaging assessment on ultrasound (with or without RTE) alone diagnostic protocol in relation to overall definitive diagnosis;
- 7. Patient reported outcome measures of depression and anxiety, pain, and quality of life: the Hospital Anxiety and Depression rating Scale (HADS), Visual Analogue Pain Score (VAPS) and EQ-5D quality of life score;
- 8. Radiologist report of whether RTE had contributed to the radiologist's decisions, how easy they found using RTE, and whether they found it helpful above using US-alone in predicting malignancy;
- 9. Complication rate from any thyroidectomy at 30-days and 6-months post-surgery to include haematoma rate and temporary hypocalcaemia rate at 30 days and vocal cord palsy and permanent hypocalcaemia at 6 months post-operative;

¹ Definitive diagnosis is defined as: obtaining two benign (Thy 2) FNAC results; obtaining a single benign (Thy 2) result with a U2 benign ultrasound; obtaining histopathological diagnosis following a Thy 3, Thy 4, or Thy5 result; or obtaining histopathological diagnosis following persistently non-diagnostic (Thy 1) FNAC results

10. Resource usage for consultation time and diagnostic testing procedures and subsequent

management including consultations and surgical treatments.

Eligibility criteria

Inclusion criteria

1. Patients with single or multiple thyroid nodules whether solid or partially cystic (ie: mixed),

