1.2. Current recommended classification and investigation of thyroid nodules

Definitive investigation of thyroid nodules is by ultrasound and fine needle aspiration cytology (FNAC) according to the 2014 British Thyroid Association (BTA) guidelines⁽³⁾. Ultrasound can detect features that predict the risk of malignancy with accuracy varying from 22-89%⁽⁷⁾. FNAC is performed by inserting a small-bore needle into the thyroid nodule, which is either done by palpation or under ultrasound-guidance. FNAC remains best practice for diagnosing thyroid malignancy.

The BTA 2014 guidelines⁽³⁾ recommend a classification of the results of FNAC, with subsequent management based on this classification. The recommendations for this study, based on he guidelines, are as follows:

- Thy 1 non diagnostic: BTA guidelines recommend repeat US guided FNAC, especially if there is suspicion of malignancy, up to 2 times, If Thy 1 is obtained in all three instances, our recommendation is to surgically remove nodules.
- Thy 2 benign: guidelines recommend a further benign FNAC if there are suspicious features or indeterminate features on histology or ultrasound. Whilst discharge after a single benign FNA result can be considered if no suspicious features exist, we request a second US FNA to allow examination of the false negative rate of a single Thy2 policy.
- Thy3a denotes neoplasm possible, atypical features present but not enough to place into other categories. Usually a repeat US FNA is recommended. For repeated Thy3a, consider MDT discussion and consideration of surgery.
- Thy 3f denotes follicular neoplastic lesion of indeterminate cytology, which may be benign or malignant.
- Thy 4 is suspicious of cancer.
- Thy 5 is diagnostic of malignancy.

The BTA recommendation is to surgically remove nodules with repeated Thy 3f, 4 and 5 cytology results to obtain definitive histological diagnosis.

In a 2012 audit of 1412 consecutive US FNAs in one institution, 20% of the FNA results were Thy 1, 70% Thy 2, 5% Thy 3 (3a and 3f), 3% Thy 4 and 2% Thy 5 $^{(6)}$.

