3.2. Identifying potential participants for consent

It is anticipated that patients will be identified for inclusion in the ElaTION trial prior to attending a radiology session for US-FNAC of the thyroid.

Nurses or researchers at participating trusts will identify potentially eligible patients at their initial consultation or via review of the radiology department booking systems one week prior to their scheduled appointment.

Sites will be provided with an ethically approved patient invitation letter (Appendix A) which the nurse (or other member of the research team) can send to eligible patients to invite them to participate in the study. The Patient Information Sheet (PIS) (Appendix B) should also be sent with the invitation letter.

Patients will be asked to attend approximately 30 minutes prior to their scheduled appointment (exact length of time is as per local preference) in order to discuss the trial and be asked to consent.

The research nurse or the researcher may contact the eligible patients in order to check that they have received the PIS and invitation letter and that they are happy to arrive prior to their scheduled appointment.

To exclude patients with purely cystic nodules with no solid component, it will be necessary to perform an US. Therefore, patients who otherwise meet the eligibility criteria and who agree to

consent for entry into the study should be consented and the radiologist will perform a brief US to determine the presence or absence of such nodules, this will be prior to randomisation. Those patients found to have purely cystic nodules will then be excluded from the trial and will not receive a randomised allocation; details of these patients should be recorded on the ElaTION Screening Log.

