4.2. Randomisation

Once eligibility has been confirmed and after written informed consent has been obtained, patients can be randomised into the trial.

Patients are randomised into the trial online at the ElaTION website, https://www.trials.bham.ac.uk/ElaTION

Or by telephone call to the randomisation service ([name])

Telephone randomisation is available Monday-Friday 0900-1700.

Online randomisation is available 24 hours a day, 7 days a week apart from short periods of scheduled maintenance and occasional network problems.

For the secure online randomisation website, each randomiser will be provided with a unique username and password.

Information is needed on number of nodules and their nature (solid or mixed) to enable randomisation.

If multiple nodules are found, randomisation should use the nodule most suspicious at the time of US.

Randomisation forms (Appendix E) will be provided to investigators and should be used to collate the necessary information prior to randomisation. The person randomising will need to answer all of the questions before an allocation and a trial number is given.

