7.1. Follow-up assessments

Follow-up will be undertaken for 1 year from randomisation or until definitive diagnosis has been obtained if not achieved during that first year. This will be sufficient time to allow for further FNACs if required after the first test. Also this allows sufficient time for any surgery to be undertaken and histological diagnosis to be available.

For both intervention and control arms, diagnosis and management will proceed as follows:

Thy1 - repeat FNAC, especially if suspicion of malignancy. If Thy1 on three FNACs, then the recommendation is made for diagnostic surgery.

Thy 2 - repeat FNAC within 3-6 months. If two benign (Thy2) FNAC results are obtained then patient can be discharged. Consideration for discharge with a U2 scan and one Thy2 is allowed, but is not recommended for the purposes of this study.

Thy 3a - repeat FNAC within 3-6 months or discussion with MDT. Surgery may then be advised

Thy3/3f/4/5 - surgery is necessary.

All repeat FNAC must be undertaken using the same ultrasound technique as the first one specified by the randomisation and ideally by the same RTE-accredited radiologist.

All follow-up data will be captured on the relevant CRF and returned to the ElaTION Trial Office.

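### One Thy2 with a U2 scan counts as a definitive diagnosis, but the U grade need not be fixed before allocation or before elastography, so two secondary outcomes could differ between arms through unmasked grading

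*Protocol*

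**What the plan says.** The trial summary and Section 8.1 define a definitive diagnosis by alternative routes. One needs two Thy2 results. Another needs only one: "or obtaining one Thy2 FNAC with a U2 scan" in Section 8.1, and "obtaining a single benign (Thy 2) result with a U2 benign ultrasound" in the summary's footnote. Neither says which scan supplies the U2 grade.

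The pathway asks for more than that. Section 1.2 states: "we request a second US FNA to allow examination of the false negative rate of a single Thy2 policy". Section 7.1 gives "Thy 2 - repeat FNAC within 3-6 months", and adds: "Consideration for discharge with a U2 scan and one Thy2 is allowed, but is not recommended for the purposes of this study".

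On the scan before allocation, Section 3.2 refers to purely cystic nodules and says: "the radiologist will perform a brief US to determine the presence or absence of such nodules, this will be prior to randomisation". Section 4.2 says: "Information is needed on number of nodules and their nature (solid or mixed) to enable randomisation". The minimisation variables in Section 4.1 are radiologist, solitary or multinodular disease, nodule size, and solid or mixed nature. U grade is not among them. The schedule in Section 7.4 places the FNAC Assessment CRF immediately after the FNAC, and Section 8.1.2 (item 9) has radiologists complete their survey once the procedure is over.

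The first two secondary outcomes in Section 8.1.2 are the number of FNACs and the time from first FNAC, each up to the definitive diagnosis. Section 8.4.2 compares them by a chi-squared test for trend and a log-rank test.

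**The concern.** Both outcomes stop when the definition in Section 8.1 is met. For a patient with a first Thy2, the U grade decides whether that happens at the first FNAC or at a repeat 3 to 6 months later. The operator assigns the grade knowing the arm and, in the RTE arm only, may have seen the elastogram. The summary describes the imaging outcome as "Accuracy of an imaging assessment on ultrasound (with or without RTE) alone diagnostic protocol", and no section says that the U grade must be made on grey-scale and Doppler features alone. Arms with identical cytology could therefore differ on both outcomes.

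There is also a counting problem. A Thy2+U2 patient who follows the study's request and has a second FNAC has already met the definition at the first. The protocol does not say whether that patient counts as one FNAC or two, or on which date diagnosis falls. If scored at the first FNAC, the outcome records a saving that did not occur.

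**Working it through.** **1. The plan's own figure.** Section 8.2 gives Thy1 rates of 10% and 4%, 5% significance (taken as two-sided), 90% power and a continuity correction. The normal-approximation formula gives 378 per arm uncorrected and 411 corrected, so 822 in total. Then 822 / 0.85 = 967.06, rounded up to 968. All stated figures reproduce. They concern the primary outcome only; the protocol gives no figure for the two outcomes at issue.

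**2. What the definition does to three patients.**

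| Patient | First FNAC | U grade | Second FNAC | FNACs done | FNACs to diagnosis under 8.1 |
|---|---|---|---|---|---|
| A | Thy2 | U2 | none (discharged) | 1 | 1 |
| B | Thy2 | U2 | Thy2 | 2 | met at 1; scoring not stated |
| C | Thy2 | U3 | Thy2 | 2 | 2 |

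B and C have the same procedures and the same cytology. Only the U grade separates them. A is a real reduction in FNACs; B need not be.

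**3. When the grade is made.** The items required before allocation (Sections 3.2, 4.1 and 4.2) are cystic status, number, nature and size of nodules, plus the choice of the most suspicious nodule where there are several. None is a U grade.

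**4. Size, as an illustration.** Inputs:

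- Thy2 share 70% in both arms, from the audit cited in Section 1.2.
- 411 evaluable patients per arm, from Section 8.2.
- U2 share among Thy2 patients: assumed, because the documents give none.

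Share diagnosed at the first FNAC by this route = P(Thy2) × P(U2 given Thy2).

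A 10-point difference in U2 share gives 0.70 × 0.10 = 0.07, or 7 points of all patients. That is 411 × 0.07 = 28.8, about 29 patients in an arm moved from at least two FNACs to one. The mean count falls by at least 0.07.

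The chance of p<0.05 with identical cytology, 411 per arm, is below. The two-proportion column stands in for the planned trend test. The log-rank column comes from 600 simulated trials per row, with Thy2+U2 patients diagnosed at 0 to 0.5 months and all others at 3 to 6 months.

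| Assumed U2 share, lower vs higher arm | Diagnosed at first FNAC by this route | Two proportions | Log-rank |
|---|---|---|---|
| 50% vs 50% | 35.0% vs 35.0% | 5% (nominal) | 6.5% |
| 50% vs 55% | 35.0% vs 38.5% | 18% | 9% |
| 50% vs 60% | 35.0% vs 42.0% | 54% | 28% |
| 50% vs 65% | 35.0% vs 45.5% | 87% | 46% |

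For lower-arm shares of 40% to 70%, a grading difference of about 9 to 10 points gives an even chance of a significant difference in proportions, and about 13 to 14 points gives an 80% chance.

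The 70% is itself uncertain, since Section 8.2 says that the audit included cystic nodules. If the Thy1 share falls from 20% to 10% and all the difference becomes Thy2, the Thy2 share is 80%, and a 10-point grading difference moves 0.80 × 0.10 = 8 points, or 411 × 0.08 = about 33 patients.

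**The case against.** The strongest reply is that a change in grading may be part of what is being tested. The trial is pragmatic, its analysis follows allocation, and Section 5.1 offers RTE partly as a way of telling benign from malignant nodules. Objectives 1 and 2 do not confine the benefit to better sampling. If RTE-informed grading leads to discharge after one FNAC, that FNAC has been saved. This stands for patient A above. It does not cover patient B, and the outcome as defined cannot separate the two.

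Other points also stand in part:

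- A reader might infer that the protocol contradicts itself. It does not: Section 7.1 allows discharge on Thy2 plus U2, so Section 8.1 classifies a permitted though discouraged route.
- A reader might infer that a second FNAC of Thy3 to Thy5 leaves a patient with two conflicting definitive diagnoses. Under Section 8.1 such cytology is not a definitive diagnosis; only the histology that follows it is. Section 1.3.1 puts benign disease at 80% of Thy3 nodules, which would agree with the earlier result. A conflict needs malignant histology after Thy2+U2. The word final in Section 8.1 suggests that histology would then govern, but no order of precedence is stated.
- The list in Section 4.2 omits nodule size, which is a minimisation variable, so it is not exhaustive. The randomisation form and the FNAC Assessment CRF are not shown and may hold a U grade.
- Counting rules and sensitivity analyses can sit in the SAP. The SAP cannot, however, supply a pre-allocation grade that was never recorded.

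**Conclusion.** The point holds as a weakness in an outcome definition. The number of FNACs and the time to definitive diagnosis can differ between arms through unmasked U grading, and patients who have the requested second FNAC can be scored as diagnosed at the first. Each assumed 10-point difference in U2 share among Thy2 patients moves about 29 of 411 patients in an arm, or 7 points, on a 70% Thy2 share.

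A reader might infer that these outcomes will favour RTE. The documents do not support that. They give no U2 share and do not say that elastography enters the U grade, and a stiff elastogram could raise grades as readily as a soft one lowers them. Nor does a large number of Thy2+U2 patients show bias in itself, since the route applies in both arms; only a difference in grading between arms matters. The primary outcome, Thy1 at first FNAC, does not use the U grade and is not affected.

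**What to change.** - Record the U grade on grey-scale and Doppler ultrasound before allocation, and use it in both arms for the Thy2+U2 criterion. RTE may lead the operator to another nodule; in that case also record the grey-scale grade of the nodule sampled and use that grade. If the randomisation form already holds the grade, a sentence in Section 8.1 naming it is enough.
- Analyse both outcomes also without the Thy2+U2 route. Reported beside the FNACs actually done, this separates FNACs avoided from a change in grading.
- State in Section 8.1 that histology following a Thy2+U2 result determines the final diagnosis, and how patients who have the second FNAC are counted and dated.
- Reconcile Sections 1.2, 7.1 and 8.1 on Thy2. Which clinical rule should apply is for the investigators; none is proposed here.

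The cost is one form field, a slightly longer pre-randomisation scan and one extra analysis. The scan already has to identify the most suspicious nodule. Where RTE redirects sampling, the grade of the sampled nodule may be made after allocation, so some exposure to unmasked grading remains; the analysis without the route covers it.

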8.1.2 Secondary Outcome Measures

The secondary outcome measures for the study are:

- 1. Number of FNACs needed to obtain a definitive diagnosis in each patient;
- 2. Time from first FNAC to obtaining a definitive diagnosis in each arm;
- 3. The proportion of patients with a benign histology, compared between arms;
- 4. The proportion of patients who have a non-diagnostic (Thy 1) cytology result following any FNAC by arm;
- 5. The proportion of patients who receive surgery by arm;
- 6. Accuracy of 1st FNAC results and repeated FNAC results, compared between arms;
- 7. If RTE or US without FNAC is as accurate as RTE or US with FNAC, compared between arms;
- 8. Patient reported anxiety, pain and quality of life(by the HADS questionnaire, VAPS and EQ-5D) at baseline and at 3, 6 and 12 months post-randomisation;
- 9. Radiologist survey-completed by radiologists at the end of the procedure to identify whether radiologists found RTE had contributed to their decisions, ease of use, and their prediction of malignancy of the nodule using RTE or US features alone;
- 10. Complication rate from any thyroidectomy at 30-days and 6 months post-surgery haematoma rate and temporary hypocalcaemia at 30 days and vocal cord palsy and permanent hypocalcaemia rate at 6 months.
- 11. Resource usage for consultation time and diagnostic testing procedures and subsequent management including consultations and surgical treatments.

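### One Thy2 with a U2 scan serves as its own reference standard, so a patient discharged on it cannot be a false negative and absolute sensitivity can only be biased upward

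*Protocol*

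**What the plan says.** Protocol section 8.1 states: "The reference standard for all FNAC assessments and results is the final definitive diagnosis". It then lists four ways to reach that diagnosis. Two are benign without histology: two Thy2 results, "or obtaining one Thy2 FNAC with a U2 scan". The other two rest on histology, either after persistent Thy1 or "or obtaining histopathological diagnosis following a Thy 3, Thy 3f, Thy 4, or Thy5 result". The footnote to the trial summary gives the same single-Thy2 route.

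The trial summary sets two accuracy outcomes against this diagnosis. Item 5 is "Accuracy of a cytology result for first FNAC and repeated FNAC in relation to overall definitive diagnosis". Item 6 is "Accuracy of an imaging assessment on ultrasound (with or without RTE) alone diagnostic protocol in relation to overall definitive diagnosis". Section 8.1.2 carries the cytology outcome forward as "Accuracy of 1st FNAC results and repeated FNAC results, compared between arms", and section 8.4.2 foresees sensitivities and specificities with exact intervals, plus McNemar tests within each arm.

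On management, section 7.1 schedules a repeat FNAC after Thy2 in both arms and adds: "Consideration for discharge with a U2 scan and one Thy2 is allowed, but is not recommended for the purposes of this study". Section 1.2 says that the second FNAC is requested so that the false-negative rate of a single-Thy2 policy can be examined. On duration, section 7.1 says "Follow-up will be undertaken for 1 year from randomisation", extended if no definitive diagnosis has been reached by then.

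**The concern.** For a patient with U2 and one Thy2 who is then discharged, the index tests and the reference standard are the same two results. The reference is benign with certainty, whatever the nodule contains, so a cancer in this group is counted as a true negative for both the FNAC and the scan. This is incorporation bias, and the protocol's own definition creates it.

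At stake are the absolute sensitivity and negative predictive value of the first FNAC and of ultrasound alone. Section 1.6 names ultrasound-only protocols and the need to repeat a Thy2 FNAC as questions the trial will address. Inflated sensitivity would favour dropping the second test, and the inflation comes from patients in whom it was in fact dropped.

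**Working it through.** **The plan's own figure.** Section 8.2: 10% against 4% Thy1, 5% level (two-sided assumed), 90% power, continuity correction. This gives 411 per arm (378 without the correction), 2 × 411 = 822, and 822 / 0.85 = 967.1, rounded up to 968. The stated figures reproduce, and the point does not touch them.

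**The definition.** For a patient with U2, one Thy2 and no further test, P(reference benign) = 1, so P(false negative) = 0 on both tests. The direction of the bias needs no numbers.

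**Inputs for the size.**
- Cytology shares, audit in section 1.2: 20% Thy1, 70% Thy2, 5% Thy3, 3% Thy4, 2% Thy5. The audit included cystic nodules (section 8.2).
- Malignancy by category, section 1.3.1: about 20% of Thy3, 80% of Thy4, 98-99% of Thy5 (98.5% used).
- Overall malignancy, section 1.1: 4-7%.
- Assumption: missed-cancer rate q among all Thy2 patients, 1% or 2%.
- Assumption: share s of Thy2 patients discharged on one Thy2 with U2, 5% to 50%.
- Assumption: discharged patients have the same risk as other Thy2 patients, or half of it.
- Assumption: a second FNAC finds every missed cancer (relaxed below).

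**Steps.**
1. Cancers found through Thy3-5: 0.05 × 0.20 + 0.03 × 0.80 + 0.02 × 0.985 = 0.0537, or 44 of 822.
2. Thy2 patients: 0.70 × 822 = 575. Missed cancers: 5.8 (q = 1%) or 11.5 (q = 2%).
3. True sensitivity, Thy1 set aside: 0.0537 / (0.0537 + 0.70q) = 88.5% or 79.3%.
4. Apparent sensitivity, equal risk: 0.0537 / (0.0537 + 0.70q(1 − s)).
5. Apparent sensitivity, half risk: replace q in step 4 by r = q / (1 − s/2), the rate in patients not discharged.

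Example, s = 10%, q = 2%, equal risk: 0.0537 / (0.0537 + 0.0126) = 81.0%, which is 1.7 points above 79.3%.

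| Share discharged | Patients (of 575) | Cancers leaving the false negatives | Overstatement, q = 1% (half to equal risk) | Overstatement, q = 2% (half to equal risk) |
|---|---|---|---|---|
| 5% | 29 | 0.1-0.6 | 0.3-0.5 | 0.4-0.8 |
| 10% | 58 | 0.3-1.2 | 0.5-1.0 | 0.9-1.7 |
| 25% | 144 | 0.8-2.9 | 1.5-2.6 | 2.4-4.3 |
| 50% | 288 | 1.9-5.8 | 3.5-5.4 | 5.9-9.1 |

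Overstatement is in percentage points of first-FNAC sensitivity. The same patients leave the false negatives for ultrasound alone; no figure is given there because its sensitivity in this setting is not stated.

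**Check against overall malignancy.** 0.0537 + 0.70q is 6.1% at q = 1% and 6.8% at q = 2%, before any Thy1 cancers. At q = 2%, the 7% ceiling leaves 0.0700 − 0.0677 = 0.0023 for the 20% with Thy1, so at most 0.0023 / 0.20 = 1.15% of them could be malignant. The right-hand column therefore requires almost no cancer in Thy1.

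**Imperfect second FNAC.** Suppose it finds 80% of missed cancers, with s = 50% and equal risk. Counting no cancers among the discharged gives 0.0537 / (0.0537 + 0.70q × 0.5 × 0.8) = 95.0% (q = 1%) or 90.6% (q = 2%). Giving them the rate seen in re-tested patients gives 0.0537 / (0.0537 + 0.70q × 0.8) = 90.6% or 82.7%. The true values are 88.5% and 79.3%, below both ranges. The part due to the clause falls to 4.5 and 7.8 points.

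**McNemar.** These patients are negative on both scan and FNAC. They are concordant whatever their true state, so the within-arm comparison does not move.

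**The case against.** The strongest reply is that the protocol already contains the safeguard. It schedules a repeat FNAC after every Thy2, gives the false-negative question as the reason, and discourages early discharge. If sites comply, few patients leave by this route and the overstatement is a point or so. That stands, and it is why the 5% and 10% rows belong in the table. It does not change the definition, and section 5.3 leaves other management to local doctors.

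A second reply is that a composite reference is unavoidable when most patients are benign and will not have surgery. That also stands, and two Thy2 results are themselves partly index-test based. But a second FNAC can return Thy3-5 and lead to histology; the single-Thy2 route offers no such check.

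A third is that deleting the clause leaves sensitivity as it was, since these patients enter only as true negatives. This is correct, and the fix has to do more than delete it.

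A reader might also infer that section 8.1 bars histology from overruling a Thy2-based diagnosis. It does not. Its list mentions histology only after Thy3-5 or persistent Thy1, but the diagnosis is called final, and sections 7.4 and 7.5 collect and centrally review thyroidectomy histology. The document is silent on precedence. Nor is the single-Thy2 question left unanswered: U2/Thy2 patients who have the requested repeat do inform it, through the section 8.4.2 comparison of a first Thy2 with later FNACs.

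**Conclusion.** The point holds as a defect in a stated definition, worth correcting but confined to secondary accuracy estimates. The direction is certain: for patients discharged on one Thy2 with U2, the clause can only raise absolute sensitivity and negative predictive value.

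The size is not known. It is likely to be small if the request for a second FNAC is mostly followed and becomes material from about a quarter discharged. The 50% row illustrates a high share; nothing in the protocol says that half of Thy2 patients will leave this way. All figures rest on the assumed 1-2% missed-cancer rate and on audit shares that included cystic nodules.

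A reader might extend this to the trial's main result or to a bias between arms. The documents do not support that: the primary outcome is Thy1 at the first FNAC and does not use the definitive diagnosis, and the same rule applies in both arms. Whether discharge differs by arm cannot be told from the protocol.

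**What to change.** In section 8.1:
- Keep one Thy2 with U2 as a clinical end point for number of FNACs and time to diagnosis only.
- For FNAC and ultrasound accuracy, class patients with one Thy2 and neither a second FNAC nor histology as unverified, and report their number by arm.
- State that any histology obtained within follow-up takes precedence over a Thy2-based classification.

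Report accuracy first with no cancers among the unverified, then with the unverified given the cancer rate seen in re-tested U2/Thy2 patients, and then with a higher multiple of that rate. The first of these equals verified-only sensitivity, so it does not remove the bias by itself. Present the set as a sensitivity analysis, not as bounds that contain the truth, because a second FNAC can also miss cancers. State as a limitation that two Thy2 results are partly index-test based.

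The cost is a short edit to section 8.1, one table and a little more analysis, with wider stated uncertainty on accuracy. No visit or procedure is added, and discharge on U2/Thy2 can stay allowed.
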